8.2.2.1. Secondary Endpoints

Although the method of analysis for the secondary endpoints is the same as the one established for the key secondary endpoints and that for SANDE at week 4 is the same of the one used for the primary endpoint, the results of the analyses on the secondary endpoints are to be interpreted as descriptive in nature, since no adjustment of the overall alpha level has been applied for taking care of these endpoints.

Mean change from baseline in Schirmer-I score without anesthesia in the Study Eye at Week 8

Actual values and changes from baseline to Week 8 in Schirmer-I score without anesthesia will be summarized by means of descriptive statistics for the Study Eye. The comparisons between each active treatment and vehicle at week 8 will be performed using the same ANCOVA model and imputation strategy described in [Section 8.2.1.2](#) for the comparisons at week 4; consequently, the point estimates, corresponding 95% CIs and p-values described in that section will be provided also for the week 8 timepoint.

Proportion of patients improving to Schirmer-I test without anesthesia ≥ 10 mm/5min in the Study Eye at week 8

Patients will be categorized into two levels: result ≥ 10 mm/5min in the Study Eye and result < 10 mm/5min in the Study Eye. The derived binary variable will then be summarized at Week 8 in a frequency table.

The comparisons between each active treatment and vehicle at week 8 will be performed using the same logistic model and imputation strategy described in section 8.2.1.1 for the comparisons at week 4; consequently, the point estimates, corresponding 95% CIs and p-values described in that section will be provided also for the week 8 timepoint.

Mean change from baseline in fluorescein tear break-up time (fTBUT) in Study Eye at weeks 4 and 8

The fTBUT will be measured twice during the first minute after the instillation of the fluorescein. If the 2 readings differ by more than 2 seconds, then a third reading is taken. The fTBUT value (in seconds) will be set to the average of the 2 or 3 measurements.

Actual values and changes from baseline to Week 4 and Week 8 in fTBUT will be summarized by means of descriptive statistics for the Study Eye.

The ANCOVA model described in [Section 8.2.1.2](#) and the imputation strategy described in [Section 8.1.1](#) will be applied to fTBUT in Study Eye at Week 4 and Week 8 separately.

Mean change from baseline in total CCI [REDACTED] in the Study Eye as assessed by the investigator at week 8

Actual values and changes from baseline to Week 8 in total CCI [REDACTED] will be summarized by means of descriptive statistics for the Study Eye.

The ANCOVA model and the imputation strategy described in [Section 8.2.1.2](#) will be applied to the change from baseline of total CCI scale in Study Eye at Week 8.

Mean change from baseline in symptoms questionnaire (SANDE) scores for severity and frequency at weeks 4 and 8

Actual observed values and changes from baseline to Week 4 and Week 8 in SANDE scores for severity and frequency will be summarized by means of descriptive statistics.

The ANCOVA model described in [Section 8.2.1.2](#) and the imputation strategy described in [Section 8.1.1](#) will be applied to SANDE symptoms questionnaire severity scores and frequency scores in Study Eye at Week 4 and Week 8 separately.

Mean change from baseline in symptoms of dry eye assessed by SANDE Global Score at week 4

Actual observed values and changes from baseline to Week 4 in SANDE Global Score will be summarized by means of descriptive statistics.

Comparisons between each active treatment and vehicle will be performed within the MMRM model described for the primary endpoint (see [Section 8.1](#)) to maintain the results consistent. For this reason, the same strategy used for the ICEs established for the primary endpoint will also be applied to this endpoint regardless of being secondary only.

Mean change from baseline of the CCI at weeks 4 and 8

CCI The score for each subscale is defined as sum of scores divided by number of questions answered within each subscale. The percentage values will be divided by 10 before applying the algorithm. Symptom relief is not assessed at Baseline.

CCI will be calculated as the sum of the scores for CCI intensity at 24 hours and 2 weeks (questions 4-9) divided by the number of questions answered for questions 4-9. CCI has a score range of 0-10.

Actual values and changes from baseline to Week 4 and Week 8 in Ocular Pain Score (assessed by OPAS questionnaire) will be summarized by means of descriptive statistics.

The ANCOVA model and the imputation strategy described in [Section 8.2.1.2](#) will be applied to the CCI at Weeks 4 and 8 separately.

The score of each domain will also be shown and summarized by means of descriptive statistics on the actual observed values (i.e. no imputation needed). Comparisons between each active treatment and vehicle will be performed using two-sample t-test or, if the required assumptions are not met, the two-sample Mann–Whitney U test will be used.

Mean change from baseline as assessed by the CCI QoL score at weeks 4 and 8

QoL score is calculated as the sum of the scores for QoL subscale (questions 13-19) divided by the number of questions answered for questions 13-19.

Actual values and changes from baseline to Week 4 and Week 8 in CCI QoL score will be summarized by means of descriptive statistics.

The ANCOVA model and the imputation strategy described in [Section 8.2.1.2](#) will be repeated for the CCI QoL subscale scores (score range: 0-10) in the Study Eye at Weeks 4 and 8, separately.

Mean change from baseline in BCDVA score in Study Eye at weeks 4 and 8

The BCDVA score is measured by ETDRS letter score. The score is given by the total number of letters read at 4-m distance. If 20 or more letters are read, then the score is given by the total number of letters read + 30. If less than 20 letters are read at 4-m distance, the score is given by the sum of the letters read at 4-m distance and the letters read at 1-m distance. The equivalent logMAR score is given by (Beck RW et al 2003):

$$\log MAR = 1.7 - (0.02) * (ETDRS \text{ letter score})$$

Actual values and changes from baseline to Week 4 and Week 8 in BCDVA score will be summarized by means of descriptive statistics for the Study Eye. The summary table will be presented by using both scores (ETDRS and logMAR).

The ANCOVA model and the imputation strategy described in [Section 8.2.1.2](#) will be repeated for change from baseline in BCDVA score in Study Eye at Weeks 4 and 8, separately.

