Missing data will be imputed by using a multiple imputation with copy-reference approach (see [Section 8.1.1](#)). For each imputed dataset, the change from baseline at Week 4 is derived. Patients with change from baseline at Week 4 ≥ 10 mm/5min will be considered as having improvement while patients with change from baseline at Week 4 < 10 mm/5mins will be considered as not having improvement. 95% CI on proportion of patients having improvement will be implemented by using Clopper Pearson method.

The derived binary variable described in the previous step will then be used in a logistic model as dependent variable; treatment (3 levels: rhNGF \blacksquare mcg/mL, rhNGF \blacksquare mcg/mL, and vehicle) and baseline Schirmer-I scores in the Study Eye as covariates.

Based on this modeling, the estimated proportions and corresponding two-sided 95% CI will be provided for each treatment arm; the estimated mean proportion differences, two-sided 95% CI, and corresponding one-sided p-value will be provided for each IMP group versus vehicle at Week 4.

8.2.1.2. Mean change from baseline in Schirmer-I score without anesthesia in the Study Eye at Week 4

The MI procedure described in [Section 8.2.1.1](#) will be applied to impute missing Schirmer-I scores at Week 4. Change from baseline at Week 4 will be fitted in the ANCOVA model with change from baseline at Week 4 as dependent variable, treatment (3 levels: rhNGF \blacksquare mcg/mL, rhNGF \blacksquare mcg/mL, and vehicle) and baseline Schirmer-I scores in the Study Eye as covariates.

Based on this modeling, a point estimate (the adjusted estimated treatment effect), associate SE, two-sided 95% CI, and corresponding one-sided p-value will be provided for each treatment group; a point estimate (the adjusted estimated treatment difference), associate SE, two-sided 95% CI, and corresponding one-sided p-value will be provided for each least squares (LS) mean treatment difference versus placebo at Week 4.

8.2.1.3. Mean change from baseline in total corneal fluorescein staining (NEI scale) in the Study Eye as assessed by the investigator at week 4

Corneal fluorescein staining has 5 zones and each zone has a score range of 0-3. The total score is determined by simply adding up the scores of the 5 individual zones. The range of total corneal fluorescein staining in NEI scale is 0-15. If any of the 5 individual zones has a missing score, the total score would be missing.

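### OPAS domain scores are compared without a baseline covariate, and the tested variable is not stated, although two other scores of the same questionnaire get baseline-adjusted ANCOVA

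*SAP*

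**What the plan says.** SAP 8.2.2.1 treats scores from one questionnaire in two ways.

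- **Pain score.** The SAP derives "changes from baseline to Week 4 and Week 8 in Ocular Pain Score (assessed by OPAS questionnaire"). The ANCOVA and imputation strategy of SAP 8.2.1.2 "will be applied to the CCI at Weeks 4 and 8 separately" (CCI is the sponsor's redaction label).
- **Quality-of-life score.** The same model "will be repeated for the CCI QoL subscale scores (score range: 0-10").
- **Domain scores.** "The score of each domain will also be shown and summarized by means of descriptive statistics on the actual observed values", without imputation. The test is then given: "Comparisons between each active treatment and vehicle will be performed using two-sample t-test" or, where its assumptions fail, the Mann-Whitney U test.

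The ANCOVA of SAP 8.2.1.2 has change from baseline as the outcome, with treatment and "baseline Schirmer-I scores in the Study Eye as covariates". For another score, that score's own baseline takes the place of Schirmer-I.

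One gap in baseline data is stated: "Symptom relief is not assessed at Baseline". The opening of SAP 8.2.2.1 says that secondary endpoints follow the key secondary method and that their results are descriptive, without alpha adjustment.

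**The concern.** Every other comparison with a legible method in SAP 8.2.2.1 adjusts for baseline: Schirmer-I at week 8 (mean and proportion), fTBUT, staining, SANDE severity and frequency, SANDE Global Score at week 4, pain, quality of life and BCDVA. The domain scores are the exception, and no reason is given.

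Three things are at stake, all modest:

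1. Precision is given up when the baseline is apparently already collected.
2. A chance difference in baseline severity passes into the estimated treatment difference. Randomization is stratified by site only (SAP 4.2), so the design does not balance baseline pain.
3. The analysis is not fully specified, because the tested variable is not named. The SAP also calls quality of life a subscale. If the domains include it, the same score gets two p-values by two methods, and the SAP does not say which one leads.

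**Working it through.** **The plan's own figures.** There is no power or precision figure for the domain scores. The only sample-size calculation is for SANDE at week 8: 92 per group, from changes of -28.2 (SD 26.36) and -17.4 (SD 20.29), one-sided 0.0125, 80% power. It reproduces: the difference is 10.8, and a Welch calculation with unequal SDs gives 92 per group (power 80.2%). It says nothing about the domain scores.

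**Inputs for the check.**
- Test level: two-sided 0.05 (Protocol 10.6.1, other statistical testing).
- Pre-post correlation rho of a domain score: not in the documents. Assumed 0.3 to 0.7.
- Equal variance at baseline and follow-up: assumed.

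**Variance of the treatment difference**, relative to a comparison of actual values (large-sample):
- actual values: 1
- change from baseline: 2(1 - rho)
- ANCOVA: 1 - rho²

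**Standard-error ratio to ANCOVA:**
- actual values: 1/√(1 - rho²)
- change: √[2(1 - rho)/(1 - rho²)] = √[2/(1 + rho)]

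| rho | actual values | change |
|---|---|---|
| 0.3 | 1/√0.91 = 1.0483 (+5%) | √(2/1.3) = 1.2403 (+24%) |
| 0.5 | 1/√0.75 = 1.1547 (+15%) | √(2/1.5) = 1.1547 (+15%) |
| 0.7 | 1/√0.51 = 1.4003 (+40%) | √(2/1.7) = 1.0847 (+8%) |

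Both ratios exceed 1 for every rho strictly between 0 and 1, so the direction does not depend on the assumed value or on which variable is tested.

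**The same in power terms.** Where ANCOVA would have 80% power, the unadjusted test has Φ[(1.960 + 0.842)/ratio - 1.960]. At rho 0.3 / 0.5 / 0.7 this is 76% / 68% / 52% for actual values and 62% / 68% / 73% for change. These figures do not depend on the number of patients.

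**Chance imbalance.** A baseline difference d between arms shifts the expected difference by rho × d if actual values are tested and by (rho - 1) × d if changes are tested. An arm that starts worse therefore looks too bad on actual values and too good on change. Given an imbalance of 1.96 standard errors, the two-sided type I error at rho 0.3 / 0.5 / 0.7 is 8% / 13% / 21% (actual values) or 16% / 13% / 10% (change), not 5%. Averaged over all randomizations it stays at 5%.

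These figures are for the t-test. They do not describe the Mann-Whitney fallback.

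**The case against.** The strongest reply is that this is a supplementary display. As far as the endpoint tables can be read (Protocol 3.1, SAP 3.2), the questionnaire enters as a pain-type score and a quality-of-life score, and both already get ANCOVA. Protocol 10.6.4 allows parametric or non-parametric tests for descriptive analyses, and one simple test serves every domain, including symptom relief. All of this stands and limits the importance of the point. It does not make the unadjusted test as good where a baseline exists.

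A reader might also infer four stronger things that the documents do not support:

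- **That the unadjusted test is biased.** It is not, over repeated randomizations. Only precision and the estimate given this trial's imbalance are affected.
- **That baseline is ignored altogether.** The test may be on change, since the section's endpoints and the general summaries are in terms of change. The text leaves this open.
- **That the arms are small.** Protocol Table 6 says that a form, its name redacted, is given to all and completed only by patients with a redacted condition or who have filled it in before. That this is the OPAS is an inference from the matching 24-hour and two-week intensity items. No proportion is given.
- **That every domain has a baseline.** Symptom relief does not. For the others it is inferred from that single stated exception, next to redacted text.

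The last objection concerns the remedy: a patient who first completes the form after baseline would leave the inferential comparison. Eye pain was reported by 48% of patients in an earlier study (Protocol 4.2), so such patients are plausible, and their number cannot be worked out. But they enter only through something that happened after randomization, so leaving them out of the test is arguably protective. They stay in the descriptive table.

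**Conclusion.** The point holds as a minor improvement. The domain comparison lacks a baseline covariate and does not name its tested variable, while two scores of the same questionnaire are adjusted. The precision loss is certain in direction for any correlation strictly between 0 and 1 with equal variances. Its size rests on an assumed correlation: over 0.3 to 0.7, a standard error 5% to 40% larger if actual values are tested, or 24% down to 8% if changes are. Disagreement between a domain result and the adjusted pain or quality-of-life result could come from the method alone. The results are descriptive and outside the multiplicity scheme, so nothing on the primary or key secondary endpoints changes.

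**What to change.** In SAP 8.2.2.1, for every domain with a baseline score, replace the two-sample comparison with the SAP 8.2.1.2 ANCOVA on observed data: change from baseline as outcome, treatment and the domain's own baseline score as covariates. If the assumptions fail, use a rank-based ANCOVA, so that a non-parametric fallback remains. Keep the t-test or Mann-Whitney test for symptom relief only. This also settles the tested variable, because with baseline in the model the treatment difference is the same for change and for actual value. If the domains include pain intensity or quality of life, say that the endpoint analysis already specified for those scores leads.

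The cost is a few lines of SAP text; the model is already specified for the other two scores. Patients who first complete the form after baseline do not enter the ANCOVA and are shown in the descriptive table only; report their number by arm.

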8.2.2.2. CCI

Descriptive in nature analyses will be performed CCI at each available timepoint by means of descriptive statistics. Changes from baseline or shift tables versus baseline will be summarized for all available post-baseline visits. Parametric or non-parametric tests, depending on the distribution of each parameter, will be applied. For continuous data, the normality assumption will be assessed by a visual inspection of the distributions. Additional analyses, as deemed appropriate, may be performed CCI without any need to change the present SAP.

CCI

CCI [REDACTED]

CCI [REDACTED]

[REDACTED]

[REDACTED]

[REDACTED]

CCI [REDACTED]

[REDACTED]

[REDACTED]

[REDACTED]

8.3 Additional Efficacy Endpoints

CCI [REDACTED]

[REDACTED]

[REDACTED]

[REDACTED]

8.4 Subgroup Analysis

Subgroup analyses of primary and key secondary endpoints will be performed on the following subgroups of baseline characteristics:

- Age class (\leq Median, $>$ Median)
- Race (White, Other)
- Ethnicity (Hispanic or Latino, Not Hispanic or Latino)
- Gender (Male, Female)
- Region (EU, US)
- Certain etiology of dry eye (Yes/No)
- Certain medical history (Yes/No)
- Certain concomitant medications (Yes/No)

CCI

9. Safety Analysis

All safety analyses will be based on the SAF according to the actual treatment received. No formal statistical testing will be performed for safety data.

9.1. Adverse Events

An Adverse Event (AE) is defined as any untoward medical occurrence in a patient or clinical investigation patient administered a medicinal product and which does not necessarily have a causal relationship with this treatment. An AE can therefore be any unfavorable and unintended sign (including an abnormal laboratory finding), symptom, or disease temporally associated with the use of a medicinal product, whether or not related to the medicinal product.

Treatment-emergent AEs (TEAEs) are defined as AEs that are reported or worsened on or after the first dose of IMP.

Adverse events will be coded according to latest version of MedDRA. Unless otherwise specified, AEs will be summarized by treatment arm and by SOC and PT, with SOC sorted in descending order of patient incidence and PTs within each SOC in descending order of patient incidence in Total group, for each treatment period (“On Treatment period”, “On Follow-up period” and “Overall”). If the total frequency for any 2 or more PTs is equal, the PTs will be presented in alphabetical order.

When summarizing the number and percentage of patients with an event, patients with multiple occurrences of the same AE or a continuing AE will be counted only once. Patients will be presented according to the highest severity (the strongest relationship) in the summaries by severity (of related AEs), if patients reported multiple events under the same SOC and/or PT.

Ocular TEAEs will be summarized separately from non-ocular TEAEs. Ocular TEAEs will be summarized for the Study Eye and the fellow eye. Non-ocular TEAEs will be summarized regardless of the Study Eye or the fellow eye.

By-patient listings of ocular and non-ocular AEs will be presented by treatment and ordered by site.

9.1.1. Incidence of Adverse Events

An overall summary of TEAEs including the number and percentage of patients who experience the following will be presented:

- Any TEAE
- Any TEAE Related to Study Drug
- Any Ocular TEAE
- Any Ocular TEAE Related to Study Drug
- Any Non-ocular TEAE
- Any Non-ocular TEAE Related to Study Drug
- Any AESI
- Any Ocular AESI
- Any Non-ocular AESI
- Any Serious TEAE
- Any Serious TEAE Related to Study Drug
- Any Serious Ocular TEAE
- Any Serious Ocular TEAE Related to Study Drug
- Any Serious Non-ocular TEAE
- Any Serious Non-ocular TEAE Related to Study Drug
- Any TEAE Leading to Treatment Discontinuation
- Any Ocular TEAE Leading to Treatment Discontinuation
- Any Non-ocular TEAE Leading to Treatment Discontinuation
- Any TEAE Leading to Study Discontinuation
- Any Ocular TEAE Leading to Study Discontinuation
- Any Non-ocular TEAE Leading to Study Discontinuation
- Any TEAE Leading to Death
- Any Ocular TEAE Leading to Death
- Any Non-ocular TEAE Leading to Death

A by-patient listing of all AEs will be presented by site.

9.1.2. Relationship of Adverse Events to Study Drug

Study treatment TEAEs will be summarized by SOC and PT. Study treatment related AEs are those with a relationship to study treatment of ‘Possible’, ‘Probable’, and ‘Highly Probable’ relationship based on the eCRF page. Any TEAE reported in the study having a possible, probable or highly probable relationship to study drug will be considered as an adverse drug reaction (ADR). AEs assessed as ‘None’ and ‘Unlikely’ will be considered unrelated for reporting purpose. Missing relationship will be counted as related to study treatment.

A by-patient listing of adverse drug reactions will be presented and ordered by site.

9.1.3. Unexpected Adverse Events

The classification of the TEAEs in expected/unexpected done by the Investigators and collected in the eCRF will not be analyzed (i.e. not reported in any TLFs). The Sponsor’s classification will be reported in the CSR for SAEs only, based on the Reference Safety Information presented in the current version of the IB.

9.1.4. Severity of Adverse Event

TEAEs will be rated as Mild, Moderate, or Severe based on the following criteria:

- Mild: These events do not interfere with the patient’s usual function.
- Moderate: These events interfere to some extent with the patient’s usual function.
- Severe: These events interfere significantly with the patient’s usual function. Severe events are usually incapacitating.

The adverse events with missing severity grade will be imputed as ‘Severe’. Any TEAEs will be summarized by severity and by SOC and PT. In the TEAE severity table, if a patient reports multiple occurrences of the same TEAE, only the most severe (mild < moderate < severe) occurrence will be presented.

9.1.5. Serious Adverse Events

A Serious Adverse Event (SAE) is defined as any adverse experience that, in the view of either the Investigator or Sponsor, meets any of the following criteria:

- results in death,
- is life-threatening (i.e. the patient was at immediate risk of death at the time of the event. It does not refer to an event which hypothetically might have caused death if it were more severe),
- requires inpatient hospitalization or prolongation of existing hospitalization,
- results in persistent or significant disability/incapacity,
- is a congenital anomaly/birth defect,
- is an important medical event.

Serious TEAEs will be summarized by SOC and PT.

A by-patient listing will also be provided for all SAEs and ordered by site.

9.1.6. Adverse Events (AEs) of Special Interest

The following adverse events are considered to be Adverse Events of Special Interests (AESIs) and by default shall be reported as SAEs (medically important criteria):

- AEs that caused a decrease in visual acuity of >30 ETDRS letters or > +0.6 LogMAR (compared with the last assessment of visual acuity at the last visit) lasting >1 hour
- AEs that caused a decrease in visual acuity to the level of light perception or worse lasting >1 hour
- AEs that required surgical intervention (e.g., conventional surgery, vitreous tap or biopsy with intravitreal injection of anti-infectives, or laser or retinal cryopexy with gas) to prevent permanent loss of sight
- AEs associated with severe intraocular inflammation (i.e., 4+ anterior chamber cell/flare or 4+ vitritis)
- AEs that can cause retinal vascular occlusion such as intraocular pressure > 40 mmHg
- AEs that, in the opinion of the Investigator, may require medical intervention to prevent permanent loss of sight.

AESIs will be summarized by SOC and PT.

A by-patient listing will be provided for all AESIs and ordered by site.

